7.2. Subject Exclusion Criteria

Subjects must NOT meet any of the following exclusion criteria:

- 1. History of any hypersensitivity or allergic reaction to zanamivir or other neuraminidase inhibitors (i.e., laninamivir, oseltamivir, peramivir), or to excipients of the CD388 Injection drug formulation; or history of drug-induced exfoliative skin disorders (e.g., Stevens-Johnson syndrome [SJS], erythema multiforme, or toxic epidermal necrolysis [TEN]).
- 2. History of any of the following:
 - a. Allergies, anaphylaxis, skin rashes (foods such as milk, eggs, medications, vaccines, polyethylene glycol [PEG], etc.).
 - b. Chronic immune-mediated disease, positive first-degree family history of autoimmune diseases.
 - c. Atopic dermatitis or psoriasis.
 - d. Bleeding disorder.
 - e. Psychiatric condition, seizures, hallucinations, anxiety, depression, or treatment for mental conditions.
 - f. Migraines.
 - g. Syncope, or vasovagal syndrome with injections or blood draws.
 - h. Cardiac arrythmia considered clinically significant by the Investigator.
- 3. Subjects with one or more of the following laboratory abnormalities at screening as defined by the DAIDS Table for Grading the Severity of Adult and Pediatric Adverse Events v2.1 (DAIDS 2017):
 - a. Serum creatinine, Grade ≥ 1 ($\geq 1.1 \times$ upper limit of normal [ULN]).
 - b. Pancreatic amylase or lipase, Grade $\geq 2 (\geq 1.5 \times ULN)$.
 - c. Aspartate aminotransferase (AST) or alanine aminotransferase (ALT), Grade ≥1 (≥1.25 × ULN).
 - d. Total bilirubin, Grade ≥ 1 ($\geq 1.1 \times ULN$).

- e. Any other toxicity Grade ≥2, except for Grade 2 elevations of triglycerides, low density lipoprotein cholesterol, and/or total cholesterol.
- f. Any other laboratory abnormality considered to be clinically significant by the Investigator.

Note: Retesting of abnormal laboratory values that may lead to exclusion will be allowed once without prior asking approval from the Sponsor. Retesting will take place during a scheduled or unscheduled visit during screening. Subjects with a normal value at retest may be included.

- 4. Alcohol or drug addiction in the past 2 years.
- 5. Experiencing symptoms of acute illness or chronic disease within 14 days prior to clinical research unit (CRU) check-in.
- 6. At screening, a positive result for hepatitis B virus surface antigen, hepatitis C virus antibody, or human immunodeficiency virus (HIV) antibody.
- 7. A positive result at CRU check-in for severe acute respiratory syndrome coronavirus 2 (SARS-CoV-2) by polymerase chain reaction (PCR).
- 8. Unwilling to comply with local health policy effective at the time regarding coronavirus disease 2019 (COVID-19). Full COVID-19 vaccination prior to participation is strongly recommended.
- 9. Women who are pregnant or nursing.
- 10. Received any over-the-counter (OTC) medications or nutritional supplements within 7 days, or any prescription medications within 14 days or <5 half-lives prior to dosing, whichever is longest (except for hormonal contraceptives, acetaminophen, or ibuprofen).
- 11. Current nicotine user or has quit habitual nicotine use in the 30 days prior to screening.
- 12. Received any vaccines or immunoglobulins within 28 days prior to dosing (90 days in case of intravenous immunoglobulin [IVIg] or biologics, or 14 days for COVID-19 vaccine).
- 13. Donated blood (within 56 days of screening) or plasma (within 7 days of screening) or experienced significant blood loss or significant blood draw (blood donation or blood loss of ≥500 mL) when participating in non-interventional clinical trials within 30 days prior to dosing.
- 14. Received a blood transfusion within 28 days prior to dosing.
- 15. Received any biologics within 90 days prior to dosing; or previous participation in another study (including investigational device studies) within 30 days of dosing or 5 half-lives of the study drug, whichever is longer, prior to screening (prior participation at any time in non-invasive methodology trials in which no drugs were given is acceptable).
- 16. Previous treatment with CD388.
- 17. Preplanned surgery at any time during the study.

18. The Principal Investigator (PI) considers that the volunteer should not participate in the study.

7.3. Requalification for Entry

Subjects not fulfilling the entry criteria and not randomized may be rescreened for participation with the approval of the Sponsor Medical Monitor. A subject who rescreens will receive a new screening number.

7.4. Subject Withdrawal Criteria

7.4.1. Withdrawal from Study Protocol

Subjects may withdraw consent to participate in this study at any time without penalty or loss of benefits to which the subject is otherwise entitled. Subjects who wish to withdraw completely from this clinical study should be encouraged to complete the Day 120/165 assessments. Every reasonable effort should be made to determine the reason a subject withdraws prematurely, and this information should be recorded on the appropriate page(s) of the electronic case report form (eCRF).

Subjects may be withdrawn from the study for any of the following reasons:

- Subject is unable or unwilling to continue
- Subject elects to withdraw informed consent
- Adverse event (whether or not related to study drug) that precludes further participation in the study in the judgment of an Investigator and/or Sponsor
- Protocol non-compliance
- Subject lost to follow-up, or follow-up is not possible
- The Investigator considers that it is in the subject's best interest not to continue participation in the study

If a subject is removed from the study for any reason, the subject will be followed for resolution of any ongoing AE(s).

7.5. Replacement of Subjects

Subjects who are withdrawn for reasons other than AEs may be replaced at the discretion of the Sponsor into the same cohort and blinded treatment assignment as the replaced subject.

7.6. Temporary Study Halt for Safety Review

The study will be temporarily halted, pending review of available data, if any of the following occur:

• If ≥2 subjects experience the same Grade 3 AE event or laboratory abnormality within 28 days after study drug administration, considered attributable to CD388 or cannot be attributed to another cause

- If ≥1 subject experiences a Grade 4 AE or laboratory abnormality within 28 days after study drug administration, considered attributable to CD388 or cannot be attributed to another cause
- If ≥1 subject experiences an SAE irrespective of toxicity grade within 28 days after study drug administration, considered attributable to CD388 or cannot be attributed to another cause

If it is considered appropriate to restart the study following an internal safety review, an amendment, if required, will be submitted to the FDA and IRB. The study will not restart until the amendment has been approved by the FDA and IRB.

7.7. Study Termination by Sponsor and Termination Criteria

The Sponsor reserves the right to terminate an investigational site or this clinical study at any time. Reasons for termination may include, but are not limited to, the following:

- The incidence or severity of AEs indicate a potential health hazard to subjects.
- Serious or persistent noncompliance by the Investigator with the protocol, clinical research agreement, or applicable regulatory guidelines in conducting the study.
- Institutional Review Board (IRB)/Independent Ethics Committee (IEC) decision to terminate or suspend approval for the investigation or the Investigator.
- Investigator request to withdraw from participation.
- Subject enrollment is unsatisfactory.

8. STUDY DRUG

8.1. CD388 Injection

CD388 Injection is a clear to lightly opalescent liquid essentially free of particulate matter containing the active pharmaceutical ingredient, CD388. CD388 Injection is supplied as a frozen sterile solution in single-use vials. Refer to the Pharmacy Manual for details.

CD388 Injection is administered by SQ injection at the doses described in Table 3. Dose levels to be assessed will follow an ascending single-dose regimen with the starting dose based on findings from 3-month rat and monkey toxicology studies.

8.1.1. Directions for Use

CD388 Injection should be thawed at room temperature over 30 minutes (not to exceed 24 hours) prior to drawing the dose from the vial into the syringe.

After CD388 Injection is drawn from the vial into the syringe, it must be administered within 4 hours.

8.1.2. Drug Storage

Vials of CD388 Injection are stored frozen at -20°C.

8.1.3. Dose Adjustment

Dosage adjustments of CD388 Injection in individual subjects are not allowed in this study.

8.2. Placebo Injection

Normal saline will be administered SQ as the placebo control.

8.3. Compliance

Treatment compliance for CD388 Injection/placebo will be documented in the eCRF by recording the date, administration time, and the volume of the dose of study drug administered.

8.4. Breaking the Blind

The study is a double-blind design. The Sponsor, Investigator, study site personnel, and subjects will not make any effort to determine which blinded study drug (CD388 Injection or placebo) is administered. Unblinded pharmacy personnel will be responsible for preparing syringes such that the double-blind is maintained.

Only in the case of an emergency, when knowledge of the study drug is essential for the clinical management or welfare of a specific subject, may the Investigator unblind a subject's study drug assignment.

As soon as possible and without revealing the subject's study drug assignment (unless important to the safety of subjects remaining in the study), the Investigator must notify the Sponsor if the blind is broken for any reason. The Investigator will record in source documentation the date and reason for revealing the blinded study drug assignment for that subject.

As PK samples from subjects assigned to placebo treatment will not be analyzed for determination of CD388 concentrations, the bioanalytical laboratory will receive the randomization list to allow for correct selection of the samples. Unblinding of the randomized treatment assignment will be performed at the bioanalytical laboratory. Specific procedures will be in place to ensure that randomized treatment assignment will not be revealed to anyone involved in the execution of the study.

8.5. Previous and Concomitant Medications and Substances

All medications administered within 28 days prior to study drug administration and throughout the study will be documented and recorded in the eCRF.

Subjects must refrain from OTC, herbal medications, and nutritional supplements within 7 days and prescription medications within 14 days or <5 half-lives before first study drug administration, and until after the final study visit (except for hormonal contraceptives, acetaminophen, or ibuprofen). The Investigator should consult the Sponsor's Medical Monitor for guidance regarding other medication or vaccine usage during the study.

8.6. Accountability Procedures

The pharmacy or study personnel are responsible for ensuring that a current record of CD388 Injection inventory and accountability are maintained.

A Pharmacy Monitor will be responsible for checking drug accountability at the site. Inventory records must be readily available for inspection by regulatory authorities at any time. Each shipment of study drug will require acknowledgment of receipt. Upon receipt of study drug, the pharmacy or study personnel will visually inspect the shipment and verify the number and condition of vials received. Refer to the Pharmacy Manual for additional information.

8.7. Study Drug Handling and Disposal

Unless expressly disallowed by institution rules or local regulations, used and unused vials of CD388 Injection will be retained at the study site until study drug accountability has been performed by the Pharmacy Monitor. Upon completion of the study, termination of the study, or upon written authorization from the Sponsor, all retained unused and partially used study drug will be centrally destroyed or destroyed at the site upon written authorization from Sponsor, unless expressly disallowed by local regulations. Adequate documentation to support destruction is required prior to destruction of the vials, and a certificate of destruction or written documentation that specifies the date, quantity, lot numbers, and method of destruction that is traceable to the study drug must be provided to the Sponsor. All records of disposal will be maintained by the Sponsor.

9. STUDY PROCEDURES

The Schedule of Events (Table 1) summarizes the frequency and timing of all applicable study assessments, including allowable windows for study visits and assessments/procedures. Written informed consent must be obtained before any study-related procedures are performed.

All procedures should be completed as close to the prescribed/scheduled time as possible. Any nonscheduled procedures required for urgent evaluation of safety concerns take precedence over all routine scheduled procedures.

When multiple assessments are scheduled at the same time point, perform the assessments in the following order: 12-lead ECG, vital signs, and blood sample collection.

9.1. Medical History

A complete medical history will be recorded, including demographic information (age, gender, race, and ethnicity).

9.2. Physical Examinations

A complete physical examination is required at screening. Targeted (i.e., symptom directed) physical examinations may be performed at all other indicated visits, and as clinically indicated.

9.3. Vital Signs

Vital signs include blood pressure (systolic and diastolic), heart rate, respiration rate, and oral temperature, and will be measured with the subject in a seated position for at least 3 minutes prior to measurement. Height and weight are to be measured and body mass index (BMI) calculated when indicated.

9.4. Electrocardiograms

Subjects should be resting (at least 5 minutes) and semi-recumbent for safety triplicate 12-lead ECGs. Data collection includes abnormal findings; if abnormal finding(s) are assessed as clinically significant, the finding(s) should be reported as AE(s). The Investigator is responsible for interpreting and measuring ECG data.

The screening ECG may be repeated once to confirm eligibility.

9.5. Laboratory Evaluations

Blood and urine for laboratory evaluations will be collected and analyzed at a laboratory in accordance with quality laboratory standards. Hematology, serum chemistry, coagulation, urinalysis, and other parameters to be tested are listed in Table 4.

Table 4: Clinical Laboratory Tests

Test Category	Specific Laboratory Tests		
Hematology: a	Hemoglobin	Neutrophils (absolute)	
	Hematocrit	Monocytes (absolute)	
	Erythrocyte (red blood count [RBC]) count	Eosinophils (absolute)	
	Quantitative platelet count	Lymphocytes (absolute)	
	Total leukocyte (white blood cell [WBC]) count	Basophils (absolute)	
	Mean corpuscular hemoglobin (MCH)	Mean corpuscular volume (MCV)	
Serum	Aspartate aminotransferase (AST)	Calcium	
Chemistry: ^a	Alanine aminotransferase (ALT)	CO ₂ or bicarbonate	
	Alkaline phosphatase (ALP)	Blood urea nitrogen (BUN) or urea	
	Albumin	Creatinine	
	Total bilirubin (if total bilirubin is ≥2 × ULN with no evidence of Gilbert's syndrome, then fractionate into direct and indirect bilirubin)	Glucose	
	Sodium	Chloride	
	Potassium	Lipase	
	Total protein	Lactate dehydrogenase (LDH)	
	Phosphorus	Amylase	
	Creatinine Clearance (Cockcroft-Gault)		
Lipids: b	Triglycerides	Low Density Lipoproteins (LDL)	
	Cholesterol, Total		
Coagulation: b	Activated partial thromboplastin time (aPTT)	International normalized ratio for prothrombin time (INR/PT)	
Complement Activation: b	Complement C3, C4, CH50		
Urinalysis: a	рН	Occult blood	
	Protein	Specific gravity	
	Glucose	Ketones	
	Appearance	Color	
	Bilirubin	Leukocyte esterase	
	Nitrite	Microscopic reflex if protein, nitrite, blood or leukocyte esterase are positive (WBC, RBC, epithelial cells, bacteria, casts, other findings)	
Serology:	Hepatitis B surface antigen (HBsAg) ^c	Human immunodeficiency virus (HIV) antibody ^c	
	Hepatitis C antibody ^c	Severe acute respiratory syndrome coronavirus 2 (SARS-CoV-2) polymerase chain reaction (PCR) ^d	

Pregnancy: e	Serum beta human chorionic gonadotropin (β-hCG) pregnancy test for females of childbearing potential (screening and Day 120/165 only), urine or serum test at all other specified visits	Follicle-stimulating hormone (FSH), if applicable to confirm postmenopausal status, is only required once
Other: f	Drug (opioids, benzodiazepines, barbiturates, cocaine metabolites, cannabinoids, methamphetamines, phencyclidine, amphetamine, cotinine) and alcohol screen	

- a. At each visit indicated in the Schedule of Events (Table 1).
- b. Performed at screening, and as clinically indicated (e.g., if the Investigator has concerns regarding an SAE, anti-drug antibody reaction in a subject with hypersensitivity reaction, fever, serious rash, joint/bone pain, cough, proteinuria, or clinically meaningful changes in the white cell differential or liver function tests).
- c. At screening only.
- d. If a subject develops signs and symptoms of an acute respiratory tract infection at any time during the study, COVID-19, influenza, and/or respiratory syncytial virus (RSV), nasopharyngeal rapid antigen test plus PCR will be performed.
- e. As indicated
- f. At screening and Day -1, and during the outpatient visits if vital signs are abnormal.

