1. PROTOCOL SYNOPSIS

Sponsor: Cidara Therapeutics Inc., San Diego, CA

Product Name: CD388 Injection

Active Ingredients: CD388

Protocol Title: A Phase 1, Randomized, Double-Blind, Single Ascending Dose Study to Determine the Safety, Tolerability, and Pharmacokinetics of CD388 Subcutaneous Administration in Healthy Japanese Subjects

Planned Study Centers: Single center in the United States

Phase of Development: 1

Indication: Influenza virus infection

IND Number: 155,536

Objectives and Endpoints

Objectives	Endpoints
Primary	
To determine the safety and tolerability profile of CD388 Injection when dosed by subcutaneous (SQ) administration as a single dose to healthy Japanese adult subjects.	• Incidence and severity of treatment-emergent adverse events (TEAEs), including but not limited to adverse events (AEs) and serious adverse events (SAEs) (including systemic reactogenicity/injection site reactions and hypersensitivity reactions), AEs leading to study drug discontinuation and/or study withdrawal, vital signs, 12-lead electrocardiograms (ECGs), and clinical laboratory tests (including hematology coagulation, serum chemistry, and urinalysis), after a single dose of CD388.
Secondary	
To determine the plasma pharmacokinetic (PK) profile of CD388 Injection when dosed by SQ administration as a single dose to healthy Japanese adult subjects.	• Pharmacokinetic parameters following CD388 Injection administration: maximum plasma concentration (C _{max}), time to maximum plasma concentration (T _{max}), terminal elimination half-life (t _½), apparent clearance (CL/F), apparent volume of distribution (V _Z /F), area under the plasma concentration-time curve from time 0 to time of last quantifiable sample (AUC _{0-last}), area under the plasma concentration-time curve from time 0 extrapolated to infinity (AUC _{0-∞}).
Exploratory	
• To evaluate the PK profile of CD388 in upper respiratory tract after SQ administration as a single dose to healthy Japanese adult subjects.	• Pharmacokinetic parameters following CD388 Injection administration: maximum nasopharyngeal (NP) concentration (C _{max}), time to maximum NP concentration (T _{max}), area under the NP concentration-time curve from time 0 to time of last quantifiable sample (AUC _{0-last}).

Objectives	Endpoints
Exploratory (continued)	

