1.1. Schedule of Events

Table 1: Schedule of Events

	Screening		Clinica	al Resea	Clinical Research Unit (CRU) Inpatient Stay	(CRU) I	npatient	Stay			Outpa	Outpatient CRU Visits	tU Visit	20
Day (Window)	-28 to -2	-1	1	2	3–6	L	6	11	14	30 (±3)	45 (±3)	(5±)	90 (±7)	120/165 a (±14)
Informed consent	X													
Inclusion/Exclusion criteria	X	X												
Medical history/demographics	X													
Complete physical with vital signs (BP, RR, HR, oral temperature, height, weight, BMI)	X													
Targeted physical with vital signs (BP, RR, HR, oral temperature, weight ^b)		×	×°	×	X	X			×	X	X	×	×	×
Safety ECG ^d	X	X	X			X			×	X				X
Laboratory evaluations (CBC with platelets, coagulation, serum chemistry, lipids, urinalysis)	X	X		X	X e	X			X	X	X	X	X	×
Virology screening (HBV, HCV, HIV)	X													
Virology screening (SARS-CoV-2)		×												
Serum/urine pregnancy test f	X	X								X		×	X	X
FSH (if applicable to confirm postmenopausal status)	X													
Drug/alcohol screen 8	X	X												
Randomization			X											
Dosing of study drug			X											
Reactogenicity/injection site inspection h			X	X	X									
PK sample collection i			X	X	X	X	X	X	X	X	X	X	X	X
Pharmacogenomics blood sample ^j			predose											
Exploratory biomarker samples			predose		X e									
Anti-drug antibodies			predose						X	X	X	X	X	X
Nasopharyngeal swab collection ^k			predose	X	X	X	X	X	X	X				
Assess and record AEs ¹	→													↑
Concomitant medications/procedures review m	\													↑

[figure not shown]
research unit; DAR = drug-antibody ratio; ECG = electrocardiogram; FSH = folliele-stimulating hormone; HBV = hepatitis B virus; HCV = hepatitis C virus; HIV = human Abbreviations: AEs = adverse events; BMI = body mass index; BP = blood pressure, CBC = complete blood count; COVID-19 = coronavirus disease 2019; CRU = clinical immunodeficiency virus; HR = heart rate; hr = hour; ICF = informed consent form; PK = pharmacokinetic; RR = respiration rate; SARS-CoV-2 = severe acute respiratory syndrome coronavirus 2.

Schedule of Events (continued)

- The timing of this visit is Day 120 for Cohort 1 and Day 165 for Cohorts 2 and 3. For subjects who discontinue study early, the Day 120/165 procedures should be performed.
- b. Weight should be measured at each of the outpatient visits (Days 30, 45, 60, 90, 120/165).

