- On Day 1, the targeted physical examination should be performed predose. Vital signs collection will occur predose, 6 hours postdose, and as clinically indicated, and will be measured with the subject in a seated position for at least 3 minutes prior to measurement. ပ
- A triplicate 12-lead ECG is to be performed at screening, at CRU check-in on Day -1, predose (immediately prior to study drug administration) and 6 hours postdose (±10 minutes) on Day 1, and as indicated in the schedule. Subjects are to be resting (at least 5 minutes) and semi-recumbent when ECG is being conducted. d.
- Laboratory evaluations (including exploratory biomarker samples) need to be performed once during the Day 3-6 interval on Day 4. e.
- A sensitive serum pregnancy test (\(\beta\)-human chorionic gonadotropin) is required at screening and Day 120/165 for females of childbearing potential. Urine pregnancy test may be performed at all other time points. £.
- Drug and alcohol screen is to be performed during the outpatient visits if vital signs are abnormal (see Appendix 2). ьio
- and once approximately 8-12 hours postdose, then twice daily on other indicated study days at least 6 hours apart), with any abnormal findings reported as At indicated visits, inspection of administration site and surrounding area will be performed twice daily (once between approximately 2-4 hours postdose, AEs. Reactions will be rated according to the scale provided in Table 5. þ.
- Blood samples for PK analysis will be collected predose (-24 hour window); post-dose at 2, 4, and 12 hours (each ±10 minute window); 24 hours (±30 minute window); 48 hours (±1 hour window); 72, 96, 120 hours (each ±2 hour window); and in the morning on Days 7, 9, 11, 14. Postdose samples collected at outpatient CRU visits at Days 30, 45, 60, 90, and 120/165 have the same windows (i.e., in ±days) as the visits. . 🚅
- A mandatory pharmacogenomic (DNA) blood sample will be collected once, preferably on Day 1 (collection at another time point is allowed if necessary) to allow for pharmacogenomic research related to CD388. ..
- Nasopharyngeal swab samples will be collected predose on Day 1, and on Days 2, 5, 7, 9, 11, 14, and 30. 7
- Adverse events (including influenza-like illness which will be tested for both COVID-19 and flu) will be collected for all subjects from the time of signing the ICF through the final study visit.

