6. STUDY DESIGN

6.1. Description of the Study

This is a Phase 1, single-center, prospective, randomized, double-blind study of ascending single doses of CD388 Injection administered SQ to healthy Japanese adult subjects. The goals are to assess safety, tolerability, and PK of CD388.

Subjects will be randomized to receive a single dose of CD388 or placebo administered via SQ injection (treatment assignment is blinded) according to the design in Table 3.

Table 3: Study Design

Number of Subjects (N = 27)				
Cohort: dose	CD388 (n = 21)	Placebo (n = 6)		
Cohort 1: 50 mg	7	2		
Cohort 2: 150 mg	7	2		
Cohort 3: 450 mg	7	2		

Note: A subject may not receive treatment in more than one cohort.

After 50% of Cohort 1 subjects have completed study drug administration and have undergone protocol-specified procedures and assessments for ≥10 days, the Principal Investigator (PI) and Sponsor will review blinded safety data: AEs (including systemic reactogenicity/injection site reactions, hypersensitivity reactions, and adverse events of special interest [AESIs]), vital signs, 12-lead ECGs, and clinical laboratory results (hematology, coagulation, serum chemistry, urinalysis) to determine the safety and tolerability of the study drug. The incidence and severity of AEs, and any adverse changes in vital signs, clinical laboratory findings, and ECGs will be considered when determining safety and tolerability of study drug. If the dose is determined to be safe and well tolerated ≥10 days after dosing, Cohort 2 will be enrolled. Enrollment of the remaining 50% of Cohort 1 will continue while the safety data of the first 50% of Cohort 1 is being reviewed. Similar processes will be followed for dose escalation from Cohort 2 to Cohort 3.

The Schedule of Events is presented in Table 1. All subjects will be admitted to the clinical research unit (CRU) for observation and safety assessments from Day -1 (check-in) to Day 14. Subjects will be monitored for AEs (including systemic reactogenicity/injection site reactions, hypersensitivity reactions, and AESIs) and SAEs throughout the study until the final study visit after dosing. Safety will also be assessed by physical examinations, ECGs, vital signs measurements, and laboratory evaluations (hematology, coagulation, serum chemistry, urinalysis) at various time points during and after the CRU stay. Concomitant medication use will be recorded throughout the study.

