12.3. Safety Analyses

Safety will be evaluated by presenting summaries of AEs and SAEs, ECGs, clinical laboratory evaluations (hematology, coagulation, serum chemistry, urinalysis), and vital signs. Adverse events will be coded using the Medical Dictionary for Regulatory Activities (MedDRA). The incidence of TEAEs and AESIs will be presented by System Organ Class (SOC) and Preferred Term (PT), relationship to study drug, and severity. A TEAE is defined as an AE that emerges during or after study drug administration having been absent pre-treatment, or worsens relative to the pre-treatment state, and through the final study visit. In addition, the incidence of serious TEAEs and TEAEs leading to discontinuation of study drug or from the study will be presented by SOC and PT.

Descriptive statistics for clinical laboratory test results, ECG parameters, and vital signs, and for changes from Baseline, will be presented by time point. The incidences of potentially clinically significant (PCS) clinical laboratory results, ECG parameters, and vital signs will also be summarized by time point.

A summary of the injection site evaluation will be presented. The number and percentage of subjects with any local reaction will be provided, as will the number and percentage of subjects with pain, tenderness, erythema/redness, and induration/swelling. The severity of each local reaction will also be presented.

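### Table 4 footnote b drops scheduled post-dose coagulation tests that Table 1, the primary endpoint, the escalation review and Section 12.3 all rely on

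*Protocol*

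**What the plan says.** The laboratory row of Table 1 (Section 1.1) reads "Laboratory evaluations (CBC with platelets, coagulation, serum chemistry, lipids, urinalysis". It is marked at screening, Day -1, Day 2, the Day 3–6 interval, and Days 7, 14, 30, 45, 60, 90 and 120/165. A table note says the laboratory evaluations "need to be performed once during the Day 3-6 interval on Day 4".

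Table 4 (Section 9.5) sorts the same tests into two groups by footnote. Hematology, serum chemistry and urinalysis carry footnote a: "At each visit indicated in the Schedule of Events (Table 1"). Lipids, coagulation and complement carry footnote b; the coagulation row is labelled "Coagulation: b". Footnote b reads "Performed at screening, and as clinically indicated", followed by examples such as concern over an SAE, or an anti-drug antibody reaction in a subject with hypersensitivity.

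Three other parts of the protocol depend on coagulation results:

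- The primary endpoint (Synopsis, repeated in Section 5) covers "clinical laboratory tests (including hematology coagulation, serum chemistry, and urinalysis), after a single dose of CD388".
- The blinded escalation review (Section 6.1, repeated in Section 12.7) uses "clinical laboratory results (hematology, coagulation, serum chemistry, urinalysis) to determine the safety and tolerability of the study drug".
- Section 12.3 lists coagulation among the laboratory evaluations and then states: "Descriptive statistics for clinical laboratory test results, ECG parameters, and vital signs, and for changes from Baseline, will be presented by time point". It also plans incidences of potentially clinically significant results by time point.

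**The concern.** The two tables give different instructions for the same blood test. A site or central laboratory that builds its requisitions from Table 4 would draw coagulation once, at screening, and afterwards only when an investigator had a reason to look. It would also skip the Day -1 sample. The only scheduled pre-dose value would then be the screening one, which can be up to 28 days old.

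Post-dose coagulation data collected that way come from subjects selected by their outcome, at times set by their events. They cannot support a by-time-point summary, a change from baseline or an incidence with all treated subjects as the denominator. The escalation review would have no scheduled coagulation results to examine. The temporary-halt rules in Section 7.6 respond to Grade 3 and Grade 4 laboratory abnormalities within 28 days of dosing, and an asymptomatic change in aPTT or INR cannot count towards them if no sample is taken.

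**Working it through.** The protocol states no total for coagulation samples, so there is no figure to reproduce. The check sets the two schedules side by side and counts.

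**Inputs**

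- Marked laboratory visits: Table 1, with its note placing the Day 3–6 draw on Day 4.
- Footnotes a and b: Table 4, Section 9.5.
- Subjects: 27, in three cohorts of 9 (Section 6.3).
- Escalation review: after 50% of a cohort has been followed for at least 10 days (Section 6.1).

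**Scheduled coagulation tests per subject**

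| | Table 1 | Table 4, footnote b |
|---|---|---|
| Screening | 1 | 1 |
| Day -1 | 1 | 0 |
| Days 2, 4, 7, 14 | 4 | 0 |
| Days 30, 45, 60, 90, 120/165 | 5 | 0 |
| Total | 11 | 1 |
| Post-dose | 9 | 0 |

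**Whole trial.** Table 1: 9 x 27 = 243 scheduled post-dose panels. Footnote b: 0 x 27 = 0. The 243 assumes that all 27 subjects attend every visit.

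**First escalation review.** Half of 9 is 4.5, so 4 or 5 subjects. With at least 10 days of follow-up, Days 2, 4 and 7 are available. Table 1 gives 3 x 4 = 12 to 3 x 5 = 15 post-dose results; footnote b schedules none.

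**Can both instructions hold?** One might read footnote b as adding event-driven tests to the Table 1 visits. Table 4 does not allow this comfortably: footnote a exists to say that a test follows Table 1, and coagulation does not carry it. Complement also carries footnote b and does not appear in Table 1 at all. That fits b being the class of tests that are not routinely scheduled after screening.

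**Lipids.** They carry footnote b and are also named in the Table 1 row, so the scheduling conflict and the 243-versus-0 count apply to them too. They are not named in the primary endpoint, the escalation review or the Section 12.3 laboratory list, so for lipids the problem is only a mismatch between tables.

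**The case against.** The best defence is that the site would follow Table 1. Section 9 presents that table as the summary of frequency and timing for all assessments, and Section 9.5 introduces Table 4 only as a list of parameters. The endpoint, the escalation review and the safety analysis all point the same way as Table 1, so footnote b may be a misplaced marker. On that reading all 243 panels are drawn and nothing is lost. Even on the other reading, the escalation review keeps adverse events, vital signs, ECGs, hematology including platelets, chemistry and urinalysis. No numerical coagulation threshold drives the decision, and the analyses are descriptive.

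Much of this is fair. The complete loss is one end of a range whose other end is no loss, and the escalation review would be incomplete rather than empty. What remains is that no sentence makes Table 1 prevail, and Section 9.5 sends the reader to Table 4 for coagulation by name. Nor is this a detail for the statistical analysis plan: it determines which samples exist, and that has to be settled before they are due.

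**Conclusion.** The concern holds. Table 1 and Table 4 footnote b give incompatible collection schedules for a named component of the primary safety endpoint, and nothing in the protocol reconciles them. The number of scheduled post-dose coagulation panels is 243 if Table 1 governs and 0 if footnote b governs, assuming full attendance by 27 subjects. The first escalation review has 12 to 15 scheduled post-dose results or none. The contradiction itself is certain. How much data would be lost depends on which table the site uses, which the document does not settle.

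**What to change.** Reconcile Table 4 with Table 1 in one of two ways, and state in Section 9 or 9.5 which table prevails.

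1. **If Table 1 stands:** change the marker on the coagulation row of Table 4 from b to a, and do the same for lipids. Keep footnote b for complement, which Table 1 does not list. If on-demand repeats of coagulation or lipids are still wanted, say that they are in addition to the scheduled visits.
2. **If routine post-dose coagulation is not wanted:** remove it from the Table 1 laboratory row, the primary endpoint (Synopsis and Section 5), the escalation review (Synopsis, Sections 6.1 and 12.7) and the safety analysis (Synopsis and Section 12.3), and deal with lipids in Table 1 separately.

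The first route costs two footnote markers and a clarifying sentence. It adds no visits, because Table 1 already plans these tests at visits where blood is drawn. The second means editing several sections and dropping coagulation from the primary safety data. Either way, check that the laboratory manual and requisitions match the chosen schedule.
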